# SA3: Identify Pharmacy System/Practice-Level Barriers and Facilitators for Universal Alcohol Screening/Intervention among Patients with Opioid Medications.

**SA3 rationale.** We have discussed above a number of barriers to pharmacists engaging patients regarding behavioral health. While our previous research has worked to address these barriers, the process of applying evidence-based services into real world health care settings is a paramount aspect of evidence-based implementation science and involves rigorous planning, monitoring, and evaluation 165-167 and indeed requires thoughtful preparation. Therefore, SA3 focuses on implementation planning to identify what *barriers* exist for implementing universal alcohol screening/intervention for those using opioid medications for a subsequent large-scale multi-site efficacy trial as well as eventual integration into system-level commercial pharmacy chain workflow. Likewise, this step will also identify *facilitators* to scaling alcohol screening/intervention for those who use opioid medications for a large-scale multisite trial and pharmacy system wide. To establish this information, we will employ tools from the Consolidated Framework for Implementation Research (CFIR) and organizational behavior and management. The CFIR is a multidimensional framework comprised of constructs for drawing out information related to implementing research into practice,  ranging from pre-implementation activities to post-implementation outcome analyses.  The CFIR has been employed within a variety of clinical and administrative areas, including healthcare delivery and processes redesign, quality improvement, health promotion, and disease management as well as in clinical areas including mental health, obesity, and high blood pressure. 

SA3 design and participant identification. We will implement cross-sectional one-time mixed methods key informant interviews to capture data that will inform our understanding of pharmacy system/practice-level barriers and facilitators for universal alcohol screening/intervention among patients with opioid medications. Interview participants will be identified through a purposive/snowball sampling approach. Relying on both on [name] (project coinvestigator) and [name] (project consultant) professional networks at the Kroger corporate and Nashville regional levels, our team will reach out and offer interview participation to individuals in each category of key informant (technicians, pharmacists, and corporate leaders). [name] is the national Manager of Clinical Program Development with the Kroger Health Corporate office who has been a close collaborator with [name] over the past 3 years in his NIDA CTN funded research project (CTN-0093; see letter of support). Identified interviewees will be contacted via email and/or by telephone. Interviews will take place in a location and time that is convenient and selected by the participants. The interviews will be conducted by a research assistant trained in qualitative interviewing and are anticipated to last up to 1 hour. At the close of these interviews, the research assistant will request from the participant suggestions of other individuals who would represent the specific perspective of pharmacy corporate leaders, pharmacists, and technicians. Completing the interview, participants will be provided with a \$75 gift card.

**SA3 assessment.** Prior to meeting in-person for the qualitative interview, the first step in our mixed methods assessment will involve the quantitative data collection. We will administer, via a web-based survey platform, the internally consistent reliable and factorially valid Organizational Readiness to Change Assessment (ORCA). This 77 item instrument assesses organizational readiness for implementing evidence-based practices in clinical settings. Primary domains assessed by the instrument include respondents' perceptions of strengths of evidence for the change and ability of the organization to support the change.

For the in-person portion of the interview, we will administer open-ended questions drawn and adapted from the CFIR interview guide for qualitative research. Items will be selected by the research team in collaboration with [name]. Items from the constructs set forth in Table 4 will be employed and include Intervention Characteristics, Inner Setting, Characteristics of Individuals, and Process. Our team has previously employed CFIR constructs along with the CFIR interview guide to develop an open-ended survey schedule for administration to health care professionals regarding substance use care within health care settings,  which interview results were used for system-level and community-wide intervention/ implementation planning. Also mentioned above, [name] is an expert in implementation science and has more than 20 years of experience in this area.

**Sample size.** We will recruit pharmacy technicians (N=20), pharmacists (N=20), and corporate leaders (N=20) to complete the SA3 interview. 41,42 Previous research has demonstrated sample sizes of 20 individuals or less can achieve close associations between the researcher and the participants, which will generate rich data

needed for elucidating complex relationships.41 Previous research has also demonstrated samples of approximately 12 interviews can saturation of findings.42 reach Saturation has been defined as a point beyond which no significantly new information is being obtained. Saturation will be discussed and analyzed by the research team after each interview has been completed. Lincoln and Guba's framework 174 will be used to address and meet criteria for quality and rigor in this study and involve credibility, dependability, confirmability, transferability. 174

SA3 analysis plan. For the quantitative survey items collected based on the ORCA survey, we will employ descriptive analyses as well as conduct chi square and One-Way ANOVA tests to examine differences between interviewed (pharmacy technicians. groups pharmacists, and corporate leaders). For the qualitative data, similar to SA2, the research team will follow methods recommended by Braun and Clarke that will capture associations between categories and extract and conceptualize themes. 158

Table 4. Consolid	dated Framework	for Implementation Research Constructs in SA3 Key Informant									
Survey Developm	ent										
Intervention	Evidence	Stakeholders' perceptions of the quality and validity of evidence									
Characteristics Strength and		supporting the belief that the intervention will have desired									
	Quality	outcomes.									
	Relative	Stakeholders' perception of the advantage of implementing the									
	Advantage	intervention versus an alternative solution.									
	Trialability	The ability to test the intervention on a small-scale in the									
		organization, and to be able to reverse course (undo									
		implementation) if warranted.									
	Complexity	Perceived difficulty of the intervention, reflected by duration, scope,									
		radicalness, disruptiveness, centrality, and intricacy and number of									
		steps required to implement.									
Inner Setting	Implementation	The absorptive capacity for change, shared receptivity of involved									
	Climate	individuals to an intervention, and the extent to which use of that									
		intervention will be rewarded, supported, and expected within their									
		organization.									
Relative Priority		Individuals' shared perception of the importance of the									
		implementation within the organization.									
Leadership		Commitment, involvement, and accountability of leaders and									
	Engagement	managers with the implementation.									
	Available	The level of resources dedicated for implementation and on-going									
	Resources	operations, including money, training, education, physical space,									
		and time.									
Characteristics	Knowledge and	Individuals' attitudes toward and value placed on the intervention as									
of Individuals	Beliefs about	well as familiarity with facts, truths, and principles related to the									
	the Intervention	intervention.									
Process	Engaging	Attracting and involving appropriate individuals in the									
		implementation and use of the intervention through a combined									
		strategy of social marketing, education, role modeling, training, and									
		other similar activities.									
Champions		Individuals who dedicate themselves to supporting, marketing, and									
		'driving through' an implementation overcoming indifference or									
	 	resistance that the intervention may provoke in an organization.									

The researchers will independently review the interview data and code inductively and deductively. Codes will be clustered based on their similarities into categories. The research team will meet multiple times to discuss the emergent themes.

**Timeline.** Based on our previous work in conducting clinical research with similar populations in community pharmacy settings, we estimate this study will require 3 years to complete (Table 5). Year 1 quarters (Q) 1-3 will involve receiving IRB approval and hiring/training staff. During the same time, we will undertake and complete all activities related to SA1, intervention adaptation and protocol development. Year 1 Q 2-3 will involve finalizing the assessment battery for SA2; Q3 will also involve the initiation of activities related to the small-scale

trial, including patient recruitment, intervention delivery, outcome assessments and data safety monitoring board meetings (DSMB), which will conclude in Year 3 Q1. Beginning in Year 1 Q4, we will initiate our activities related to SA3, including developing our qualitative interview schedule, participant identification, interviewing, and analyses, which will conclude Year 3 Q1. Study papers will be produced Year 1 Q3-4 and Year 3 Q2-4.

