In terms of needed time to recruit our targeted patient population, based on our data from our recently completed research study (mentioned above) at 19 Kroger sites and based on our previous screening study and small scale study, we expect to approach 9 patients for recruitment monthly at each of our pharmacy locations.  With this rate and based on our procedure mentioned above of 1:1 recruitment of individuals with risk/non-risk alcohol use, study recruitment will require approximately 13-months to complete. We have chosen to focus recruitment at a limited number of sites (N=3) during feasibility/acceptability/preliminary efficacy testing to ensure internal validity of our procedures, limiting possible site variation, and limiting multisite challenges. During screening, we will capture sex, insurance status, and age for all eligible patients to assess basic demographic differences among those who participate versus those that do not.

While definitive estimation and hypothesis testing are not the aim of this study, the target sample size will allow estimation of odds ratios via 95% confidence intervals comparing outcome rates in the intervention and control arms, while accounting for within site clustering, with lower bounds differing from the odds ratio estimate by a factor of 1/3 to 1/2 and upper bounds differing from the odds ratio estimate by a factor of 2 to 3 for a broad range of overall rates, true odds ratios, and magnitude of site-to-site effects. In particular, this study will allow detection of strong signals of preliminary benefit and provide suggestions of benefit for more subtle signals.

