We will first provide descriptive summaries of each variable measured at baseline, 2-, and 3-months overall, by risk/non-risk alcohol use, as well as by intervention group (note that all included participants are positive for co-use at baseline). Within an intent-to-treat framework, we will fit 3-level generalized linear mixed models (GLMM) to relate repeated assessments across time of the primary outcome measured (i.e. elimination of co-use) to the intervention. Additional analyses within the 3-level GLMM framework will also be conducted to assess the overall impact of the intervention on reducing percent days alcohol use among patients during the prescribed opioid treatment period. All analyses will be adjusted for covariates likely to be associated with the outcome. Specifically, this will include baseline measures such as opioid use, mental health, substance use, pain/physical function, social services utilization, and readiness to change in addition to and demographic covariates including (but not be limited to) age, sex, race, socioeconomic status, and rural/urban living. 159 Social desirability will also be included as a time varying covariate to account for the degree to which participant response bias may impact study outcomes. Random intercepts will be used to account for correlations on the patient level and pharmacy site level. We will also test risk/non-risk alcohol use as an effect modifier to determine whether the intervention has a differential impact on individuals with distinct levels of drinking; we recognize, however, the sample study sample size may limit the power of the analysis to detect changes at a probability of <0.05. Thus, it is important to note our above discussed analysis focus on 95% confidence intervals comparing outcome rates in the intervention and control arms in order to detect subtle trends in relation to intervention efficacy. Model parameters, including treatment effects at each follow-up, will be estimated using restricted maximum likelihood. 160 An advantage of this approach is treatment effect estimates remain consistent and approximately unbiased if missing data follow a missing-at-random pattern (MAR; data values are independent of the missingness mechanism conditional on the observed data), the most general data-centric missing data assumption.

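### SA3 plans group tests on the items of a 77-item survey with 20 people per group and no limit on the tests; comparing domain scores would give fewer chance findings and more power

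*Combined protocol and SAP*

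**What the plan says.** The SA3 assessment paragraph introduces the Organizational Readiness to Change Assessment (ORCA), given as a web survey before the interview: "This 77 item instrument assesses organizational readiness for implementing evidence-based practices in clinical settings". It describes the content in terms of domains: "Primary domains assessed by the instrument include respondents' perceptions of strengths of evidence for the change and ability of the organization to support the change". It gives no response format, no scoring rule and no number of scales.

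The SA3 sample size paragraph sets the groups: "We will recruit pharmacy technicians (N=20), pharmacists (N=20), and corporate leaders (N=20) to complete the SA3 interview". The number rests on qualitative saturation ("Saturation will be discussed and analyzed by the research team after each interview has been completed"). No power or precision argument is given for the survey comparisons.

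The SA3 analysis plan says that for "survey items collected based on the ORCA survey, we will employ descriptive analyses as well as conduct chi square and One-Way ANOVA tests" will be used to examine differences between the three groups. SA3 has no significance level, no rule for which items get which test, no restriction to domain scores, no multiplicity handling and no alternative for sparse tables.

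**The concern.** Read as written, the unit of testing is the item, and there are 77 of them. With that many unrestricted tests, some group differences will be flagged by chance. With 20 people per group, a single item also has little power to show a real difference, and chi-square discards the ordering of any ordinal response. The output could therefore be a short list of significant items that mixes chance findings with a few real ones.

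The Specific Aims say that SA3 is to inform how the later powered trial is carried out. A chance difference between roles could be taken up as a planning input, for example as a sign that one staff group needs separate preparation. No efficacy conclusion depends on these tests.

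**Working it through.** SA3 gives no error rate or power figure, so there is none to reproduce.

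**Inputs from the plan.** 77 items (SA3 assessment); 3 groups of 20, so 60 people (SA3 sample size).

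**Assumptions.** Alpha 0.05, with 0.01 and 0.10 as a range. The only threshold in the documents is an SA2 remark on the "power of the analysis to detect changes at a probability of <0.05". The number of response options and how evenly they are used are also assumed.

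**1. Expected chance findings.** Number of tests x alpha, if each item is tested once and no group differs:
- alpha 0.05: 77 x 0.05 = 3.85
- alpha 0.01: 77 x 0.01 = 0.77
- alpha 0.10: 77 x 0.10 = 7.7

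**2. Chance of at least one, at alpha 0.05.** With independent items, 1 - 0.95^77 = 0.981. The binomial gives 90.3% for at least two and 74.7% for at least three. Items of one instrument are usually correlated, so 77 equally correlated items were simulated with one-way ANOVA on 3 x 20 people:

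| Correlation | Mean number flagged | P(at least 1) | P(at least 2) |
|---|---|---|---|
| 0 | 3.8 | 98% | 90% |
| 0.2 | 3.8 | 94% | 80% |
| 0.4 | 3.7 | 81% | 60% |
| 0.6 | 3.8 | 60% | 42% |

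Correlation leaves the mean almost unchanged but bunches the findings: at 0.6 the median is 1 and the 90th percentile is 11.

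**3. Chi-square tables.** The expected count is 20 x the share of a response category, so a count of 5 needs a share of 25%. Four equally used options give 20/4 = 5.0; five give 20/5 = 4.0. With five options, 99.8% to 100% of simulated tables broke the guideline that no more than 20% of cells have expected counts below 5. With two options, 0% broke it at a 50/50 split, 45% at 25/75 and 79% at 20/80.

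Simulated false-positive rates at nominal 5% were:
- five options: 4.7% (even use), 4.0% (mild skew), 3.2% (skewed), 2.9% (very skewed)
- two options: 4.0% to 5.3%
- ANOVA on five-point items: 4.8% to 4.9%

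Sparse tables thus lower the rate. If five-option chi-square tests predominate, the expected number of chance findings is about 77 x 0.0285 = 2.2 to 77 x 0.047 = 3.6.

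**4. Power.** One-way ANOVA with 3 x 20 people, by the noncentral F distribution at Cohen's f = 0.4 (a large effect):
- alpha 0.05: 77.6%
- Bonferroni over 77 items, 0.05/77 = 0.00065: 21.9%
- Bonferroni over two scores, 0.05/2 = 0.025: 67.8%

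With two scores tested at 0.05, the expected number of chance findings is 2 x 0.05 = 0.10, and the family-wise error is 1 - 0.95^2 = 9.8% if they are independent. Two is illustrative.

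**5. Score against item.** In a simulation of five-point items with correlation 0.4 and a shift of 0.6 SD between the extreme groups, power at 0.05 was about 70% for a 38-item score, 33% for ANOVA on one item and 16% for chi-square on one item.

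**The case against.** The strongest reply is that the plan does not state that 77 separate tests will be run. The sentence contrasts quantitative survey items with the qualitative data that follow, so items may simply mean the survey data, and one-way ANOVA is a usual test for scale scores. SA3 is a key-informant study ("Interview participants will be identified through a purposive/snowball sampling approach"), analysed mainly by theme, and no decision rule hangs on an ORCA p-value. This stands in part. It makes the size of the problem conditional on the item-level reading, and it limits the harm to over-reading. It does not remove the point, because items are what the sentence names and nothing in SA3 narrows them.

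It may also be said that the study disclaims formal testing: "While definitive estimation and hypothesis testing are not the aim of this study". That statement sits in the SA2 sample size text, and the focus on 95% confidence intervals is in the SA2 analysis plan. SA3 repeats neither and names significance tests.

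Three stronger readings might be inferred and are not supported:
- *Many chi-square tests are invalid.* The response format is not given, and in the simulations the false-positive rate was near nominal or below it. Balanced two-option items show no fault.
- *A spurious finding is near certain.* That needs items that are independent or nearly so. The plan itself describes the instrument as internally consistent, which implies correlation.
- *Spurious differences between two named groups will be reported.* Only overall three-group tests are named; no pairwise comparison is planned.

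Nor does the plan name domain scores or give a closed list: it says the primary domains include two.

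**Conclusion.** The point holds as a low-severity weakness of analysis choice. About four chance differences are expected, provided that all 77 items are tested once at 0.05 and the groups truly do not differ. The figure scales directly with alpha and with the number of items tested, and real differences between roles would leave fewer true nulls. Sparse tables cost power and do not add false findings. Because the sampling is purposive and by referral, respondents may not be independent; these calculations do not cover that.

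The main reason to change is that a better method is available from the same data. Domain scores reduce the number of tests and use the information in many items together, whereas a correction over all 77 items would leave very little power.

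**What to change.** Replace the testing sentence in the SA3 analysis plan with one that:

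- compares the three groups on ORCA domain scores listed in advance with their scoring rule, covering evidence strength and organisational support plus any other standard ORCA scales the team chooses to list;
- reports group differences with 95% confidence intervals and labels them exploratory;
- reports individual items descriptively, without p-values.

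This costs a sentence or two of text and leaves fewer analyses to run. It needs no new data and no more participants. The downside is that no individual item is formally tested.

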# Possible Barriers to Study Success and Resolutions

We anticipate 3 primary barriers to the success of this study and have plans in place for response and/or resolution. First, critics may suggest that providing an intervention to those with non-risky alcohol use who are also taking opioid medications is unnecessary given they are at low probability for neg-

Tabl	le 5. Project Timeline		Year 1				Year 2				Year 3		
	Activity	Q1	Q2	Q3	Q4	Q1	Q2	Q3	Q4	Q1	Q2	Q3	Q4
1-3	IRB approval	Х											
	Hire staff	Х	Х	Х									
	Train staff		Х	Х									
1	Adapt intervention	Х	Х										
	Adapt/expand protocol	Х	Х										
	Finalize study protocol		Х	Х									
2	Finalize assessment battery		Х	Х									
	Patient recruitment			Х	Х	Х	Х	Х					
	Intervention delivery			Х	Х	Х	Х	Х	Х				
	Outcome assessments			Х	Х	Х	Х	Х	Х	Х			
	DSMB meetings			х	Х	Х	Х	Х	Х	Х			
	Data cleaning/analyses									Х	Х		
	Protocol paper			Х	Х								
	Main outcome paper										Х	х	Х
3	Develop qualitative interview				Х	Х							
	Identify participants					Х	Х						
	Administer survey/interview						Х	Х					
	Data analysis								Х	Х			
	Main outcome paper										Х	Х	Х
1-3	Submit final report												Х

ative consequences. It is important to recall, as reviewed/cited above, there is no empirical literature that supports this perspective—rather all-peer reviewed human and animal, governmental, packaging inserts, and professional literature available clearly state that any co-use of alcohol and opioid medications is dangerous and should be not done. Therefore, this study will specifically recruit on a 1:1 ratio those with non-risk as well as those with risky alcohol use and examine outcomes for both subgroups by intervention condition.

Second, some critics may also assert that given the BI-MTM intervention already has been developed and tested in a small-scale clinical trial, that advancing *ABI-MTM* is unnecessary and BI-MTM should be sufficient for co-use of alcohol and opioid medications. Our team deliberated over this question extensively. Opioid medication misuse is a composite set of behaviors including, for instance, using more medication than prescribed, using to get high or to cope with problems, and doctor shopping. Misuse also is frequently accompanied by a variety of concomitant conditions (i.e., mental health, illicit substance use) that together require a resource intense and comprehensive intervention. Our goal with the ABI-MTM intervention is to integrate a very brief and targeted intervention focusing only on the highly specific outcome of co-use elimination (i.e., [1] eliminating alcohol use during opioid treatment or [2] substituting a non-opioid pain therapy). Thus, ABI-MTM will be very different in practice than the BI-MTM—requiring specific adaptation efforts and preliminary testing.

Third, we do not anticipate a change in our ability to recruit participants in SA2 (i.e., pharmacy patients); however, there is a chance recruitment could slow at some point in the study. Given the hundreds of Kroger stores in Tennessee (and thousands across the US) and our close collaboration with corporate and local leaders on this project, should participant recruitment become a challenge, we have the ability to open up recruitment in other stores and/or create Kroger medication system hard stops in the store workflow that would *require* patients to be screened before leaving the stores. Based on our experience, these are highly effective tools that can be used to improve site performance. In the same vein, based on our close collaboration with corporate and local leaders, we are confident that should our sampling approach for SA3 (i.e., staff/leadership key informant interviews) prove to not meet our targets, our local and corporate partners will help assist us to identify additional possible participants who would be available and potentially interested with speaking with us.

